7.2.7 Randomisation Procedures

Not applicable.

7.2.7.1 Blinding Procedures

Not applicable.

7.2.8 Post-Investigational Medical Care

After the clinical study the subjects will be able to continue with their Investigational device. Routine controls with audiological checks will follow local routines according to the standard treatment program for bone conduction hearing implant systems. The Investigational device will be warranted and supported with service according to normal regional Cochlear routines.

7.3 Performance Evaluations and Procedures

7.3.1 Eligibility Evaluations and Procedures

Demographics

The following demographic data will be recorded at Screening and Baseline:

- Age collected as date of birth (month and year)
- Gender
- Race
- Nicotine use (Cigarettes/day)

Medical history

The following information will be recorded at Screening and Baseline:

- Relevant medical and surgical treatment during the past three years as judged by the investigator
- Current concomitant medication and treatments

Hearing history

During Screening and Baseline a number of baseline characteristics will be recorded:

- Type of hearing loss: (Conductive, Mixed or SSD)
- Aetiology of hearing loss: (chronic) infection, tumor, trauma, malformation, otosclerosis, other

Device history

- Current hearing aid (yes/no, specify model and brand, side and years of hearing aid use, reason for change)
- Previous experience from amplified sound through properly fitted amplification (specify type, duration of use, when stopped use, reasons stop using)
- Has the subject previously been suggested a bone conduction hearing implant solution? (yes/no, reason for rejection)
- Has the subject previously had a Baha implant (yes/no, reason for changing)

Treatment ear

Treatment ear (indicate left or right or both. In case of both, indicate “test ear”).

Audiogram

Unaided audiometric threshold measures (including both air- and bone conduction thresholds) should demonstrate whether the subject has a CHL, MHL or SSD and meets the audiological inclusion criteria.

An existing audiogram may be used as long as it has been completed during the last six months, and contains all the required relevant frequencies. Frequencies required for air conduction thresholds are 250, 500, 750, 1000, 1500, 2000, 3000, 4000, 6000 and 8000Hz. For bone conduction thresholds the required frequencies are 250, 500, 750, 1000, 1500, 2000, 3000, 4000 and 6000Hz. The subject's pre-operative Pure Tone Average PTA4 for CHL and MHL (*mean of 500, 1000, 2000 and 4000Hz*) using unmasked BC thresholds and the Pure Tone Average PTA4 for SSD (*mean of 500, 1000, 2000 and 3000Hz*) using air conduction thresholds should be computed and measured in order to ensure that the subject meets the inclusion criteria.

If an audiogram is older than 6 months or does not contain the required frequencies, a new audiogram shall be performed at Screening/Baseline. Frequencies required for air conduction

thresholds are 250, 500, 750, 1000, 1500, 2000, 3000, 4000, 6000 and 8000Hz. For bone conduction thresholds the required frequencies are 250, 500, 750, 1000, 1500, 2000, 3000, 4000 and 6000Hz. Contralateral masking should be used if needed, and according to local practice. The site staff shall always measure both the unmasked thresholds, as well as and the masked thresholds if applicable.

Soft tissue thickness

At Screening and Baseline or at Surgery, depending on local practice and requirements, soft tissue thickness should be measured. The measurement should be performed in the centre of the marked coil position. For complete instruction and recommendation regarding the soft tissue thickness, see the Cochlear Osia OSI200 Implant Physicians Guide (9).

7.3.2 Post-Enrolment Evaluations and Procedures

7.3.2.1 Surgery

The Cochlear Osia OSI200 Implant Physicians Guide does not take into account any particular circumstances or factors relevant to an individual patient or case. Other surgical approaches and variations are practiced and may be more appropriate in certain patient cases. After considering all relevant circumstances, factors and information in each case, the appropriate surgical procedure is determined by the responsible investigator exercising independent medical judgement. Complete information is found in the Cochlear Osia OSI200 Implant Physicians Guide (9). However, the ideal position of the OSI200 Implant is with the actuator close to and in horizontal line with the ear canal without touching the pinna (Figure 5). The ideal angulation of the implant is around 0° for the coil and the actuator (Figure 5). Depending on the anatomy and medical history of the patient the placement may vary, and the maximal deviation should be 45° for the coil or actuator (Figure 6 A and B). The transmitting range of the OSI200 Implant is dependent of the soft tissue thickness; if the soft tissue thickness is exceeding the recommended thickness it will have a negative impact on the sound processor performance and magnet retention. Take patient hair and potential use of optional Cochlear SoftWear Pad into consideration when determining if soft tissue thinning is needed.

[figure not shown]

Figure 5: Ideal OSI200 Implant placement.

[figure not shown]

Figure 6: The maximum deviation should be 45° for either the coil (A) or the actuator (B).

During surgery the following variables should be collected:

- Soft tissue thickness (mm) (if not collected already at Baseline visit)
- Type of anesthesia (general/local)
- Bone polishing/removal at the actuator site (yes/no)
- BI300 Implant length (3mm/4mm)
- Location of BI300 Implant (mm between the ear canal and the center of the actuator).
- Soft tissue reduction (yes/no)
- Surgical incision type (examples; C-shaped/S-shaped/straight)
- Location of the surgical incision in relation to the actuator (anterior/posterior)
- Estimated length of the surgical incision (mm)
- Placement of the coil (periosteal pocket (under periosteal)/on top of periosteum/on top of muscle)
- Surgery time (time between first incision to last suture)

At approximately 2 weeks after surgery, sutures should be removed.

7.3.2.2 Audiometry testing

GENERAL INSTRUCTIONS FOR AUDIOLOGICAL ASSESSMENTS

A detailed work instruction regarding the audiological assessments will be available during training before the start of the study.

Simultaneous bilateral implantation

In the case of a subject receiving simultaneous bilateral Investigational device, one of the treatment ears will be selected as the “test-ear”, tested for efficacy purposes. All tests will be

performed for the “test ear” alone and the other ear blocked. Selection of the “test ear” will be as judged by the responsible investigator prior to surgery. Patient-reported outcomes (APHAB, SSQ) and quality of life assessment (HUI), will be collected post-surgery in a bilateral hearing situation. Safety-related information, including adverse events and device deficiencies, will be collected and reported for each side receiving the Investigational device, i.e. for the whole subject.

Current hearing aid

If the subject is currently using a hearing aid at Screening/Baseline, the speech in noise test shall also be performed with the current hearing aid.

Blocking

All audiometric tests shall be performed with the non-test ear blocked (in case of normal or near-normal hearing or a large asymmetry with the non-test ear having significantly better hearing thresholds). Before blocking of the non-test ear a free-field measurement on PTA4 frequencies (500, 1000, 2000, 4000 Hz) shall be performed. The blocking shall then be done with earplug and muff and a additional free-field measurement on PTA4 frequencies shall then be performed to verify effective blockage and document the hearing level after blockage.

Settings for the Sound Processors

The Investigational device and the Baha 5 Power SP should be tested using the Everyday program.

AUDIOLOGICAL ASSESSMENTS

General set up

All tests shall be performed in a sound insulated room. Equipment used for audiological testing shall be calibrated before initiation of the study. The speakers should be at the height of the test subject’s head and more than 1 metre away from the test subject. There should preferably be more than 1 metre of free space around the test subject in all directions. This is in accordance with the current standard (16). It is important to keep the same sound room and test equipment set-up during the entire clinical study. ***Changes may be necessary and allowed, but only after approval by the Sponsor.***

Sound Processor fitting

The BFS of current market release will be used at Screening and Baseline when the fitting procedure should be performed for the Baha 5 Power Sound Processor on a Softband as a reference device.

The currently released version of OFS will be used to adjust the Investigational device settings for a specific subject. This will be performed during fitting, and throughout the study as needed (for example if the magnet is replaced with a different strength or start/stop of use of a soft pad). If the gain needs to be adjusted or changes to the program configuration are needed, a fine tuning is recommended. The fitting software will be installed on a laptop computer provided by the Sponsor, and the fitting-data will be saved on the laptop until the study is ended when it will be transferred to the Sponsor in a coded way.

Coil-to-coil measurement

The Digital Link Calibration (e.g. coil-to-coil measurement) that is a step in the connection step in the OFS, should be performed at each occasion the software is being used to fit or finetune the device to optimise the performance of the device for the user throughout the study. This will also provide an indication of the soft tissue thickness during the course of the study.

Feedback measurements

For the sound processor's Individual Stable Gain (e.g. feedback measurements as part of the FS) the feedback analyser test should be performed at each occasion the software is being used to fit or finetune the device to optimise the performance of the device for the user throughout the study. For the Investigational device this data will be collected, saved and eventually transferred to the Sponsor for analysis.

Bone Conduction (BC) Direct

BC Direct is a tool in the OFS and BFS (current versions) to establish the unmasked bone conduction threshold with tones presented through the sound processor. At Baseline, BC Direct data shall be collected with the Baha 5 Power SP on a Softband using the BFS and shall be used to calculate the fitting (settings) of the SP for the Softband test. BC Direct measurements (as part of the OFS) will also be performed from fitting to Follow up 6M when the subject is using the Investigational device. BC thresholds obtained at the following frequencies will be recorded; 250, 500, 750, 1000, 1500, 2000, 3000, 4000, 6000 Hz.

Free-field thresholds

The purpose of this test is to establish the hearing thresholds in free field through a speaker in front position (0 degrees azimuth) according to the so-called ascending or modified Hughson-Westlake method (Figure 7). The frequencies to be tested are [0.25, 0.5, 0.75, 1.0, 1.5, 2.0, 3.0, 4.0, 6.0 and 8.0 kHz], the signal to be used shall be warble tones.

At Baseline, free-field thresholds shall be measured for the unaided situation and with the Baha 5 Power Sound Processor on a Baha Softband.

At the fitting visit and at 3 and 6 months this test shall be performed with the Investigational device.

[figure not shown]

Figure 7: The setup of the speaker when testing Free-field thresholds and Speech recognition in quiet.

Speech tests

Speech recognition in quiet

The purpose of this test is to establish the test subject's ability to recognise speech in a quiet surrounding. The speech test in quiet shall be performed using phonetically balanced monosyllabic words presented in free field through a speaker from the front (0 degrees azimuth) (Figure 8). The test material shall be monosyllables and presented at 50-, 65- and 80-dB sound pressure level (SPL) and scores shall be recorded as % correctly repeated words at each presentation level. The length of the list shall be validated according to the language, preferably a 50 word list.

At Baseline the speech in quiet test shall be performed for the unaided situation and Baha 5 Power Sound Processor on a Baha Softband.

At the fitting visit and at 3 and 6 months this test shall be performed with the Investigational device.

Adaptive Speech recognition in noise

The purpose of this test is to establish the test subject's ability to recognize speech in the presence of background noise. The adaptive speech test in noise shall be conducted using validated lists for the language it is presented in. The first list shall be used as a training list before the test is performed and the training list shall be used at each visit. Both speech and noise will be presented in free field from the front speaker (0 degrees azimuth) (**Figure 8**). In Hong Kong software and speech material to be used is the CHINT (11), where the noise shall be kept constant at 65 dB SPL, and the speech shall be adapted stepwise according to the software used to establish the signal-to-noise ratio (SNR) where the test subject repeats 50% of the material correctly. In Melbourne and Sydney, the test to be used is AuSTIN (12). The sentences shall be presented at a constant level of 65 dB SPL throughout the test, and the

babble noise shall be adapted stepwise according to the software used to establish the speech-to-noise ratio (SNR) providing a 50% level of correctly repeated morphemes.

[figure not shown]

Figure 8. The setup of the speakers when testing Adaptive Speech recognition in noise.

At Baseline, the speech in noise test shall be performed for the unaided situation and Baha 5 Power sound processor on a Baha Softband. If the subject has a current hearing aid, the test shall also be performed with the hearing aid at Baseline. At the fitting visit and at 3 and 6 months this measurement shall be performed with the Investigational device.

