4.2.2.1.1 Performance

The results from the clinical investigation demonstrate the following benefits for subjects with CHL, MHL and SSD with regards to hearing performance and health related quality of life.

The Osia System provided statistically significant improvements in hearing performance compared to the unaided condition with an improvement in hearing thresholds (PTA₄, mean of 0.5, 1, 2, and 4 kHz) of 24.9 dB (SD 9.5 dB, range -50 to -6 dB, $p < 0.0001$), speech recognition in quiet at 50, 65 and 80 dB SPL of 37.9 % (SD 25.2, range -40.0 to 80.0 %), 59.8 % (SD 27.1, range -5.0 to 100.0 %) and 31.7 % (SD 32.0, range -4.0 to 100.0 %), respectively, and adaptive speech in noise (SNR) of -13.3 dB (SD 8.1, range -47.2 to 0.6 dB, $p < 0.0001$).

All SSQ parameters (Total, Speech, Spatial, and Quality) showed statistically significant improvements ($p < 0.0001$) and APHAB scores showed significant improvements ($p < 0.0001$) for the subscales Ease of Communication (EC), Background Noise (BN), Reverberation (RV), and the Global score. Health status and health related quality of life, measured with HUI3, showed statistically significant improvements for the parameters Comprehensive health state ($p = 0.035$) and Hearing attribute ($p = 0.0014$).

Comfort with the use of the Osia System, measured using a visual analogue scale where 0% was defined as no comfort at all and 100% as most comfortable imaginable, showed a total mean comfort of 81% at 3 months and the mean reported daily use was 10.5 hours/day (SD 4.3, range 1.0-18.0 hours/day).

Analysis of the separate subgroups (CHL/MHL and SSD) showed similar trends as for the entire population.

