9 STATISTICAL CONSIDERATIONS

9.1 General Considerations

The distribution of continuous variables as well as change in continuous variables will be given as n, mean, SD, SEM, Median, Min and Max and the distribution of dichotomous and categorical variables will be given as number and percentages. For continuous variables estimated mean and the 95% two-sided confidence interval (bootstrapped) for difference between groups will be presented.

Since all included subjects will have measurements of the primary and important secondary efficacy variables for unaided hearing, with the Investigational device and with a Baha Power sound processor on a Baha Softband, all statistical analyses will be paired. All statistical analyses will be non-parametric. In order to choose the most powerful test, the Fisher's non-parametric permutation test for paired observations will be used for all paired analyses of continuous variables. The permutation tests use the measured values and not only the ranks in the calculations. For paired analysis of dichotomous and ordered categorical variables the Sign test will be used.

The main efficacy analyses will be performed at 3 months after surgery on the ITT population and complementary efficacy analyses will be performed 6 months after surgery on the ITT population. In addition, all analyses will be made on the PP population. Sub analyses will also be performed on one group consisting of Mixed/conductive subjects and one consisting of SSD subjects.

Imputation of missing values will be performed for all efficacy variables using stochastic regression imputations. All ITT analyses will be performed/presented both for the imputed and for the non-imputed data (sensitivity analyses).

The final definition of the analysis sets (ITT, PP and Safety) will be taken at the clean file meeting before database lock. See separate paragraph for definitions.

A statistical analysis plan (SAP) with detailed statistical analyses specified for all variables and time points will be written and signed before the database lock.

The approximate number of subjects per site is 10 and the maximum is approximately 15. See separate paragraph for Sample size calculation.

Major protocol deviations are those that are considered to have an effect on the analysis. The number of patients with major protocol deviations will be summarised per treatment group. A list of protocol deviations will be produced.

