9.4 Sample Size Determination

Based on 6 months safety data from 51 subjects implanted with the predecessor Osia System at 5 clinics in the multicentre clinical investigation described in section 4.2.2.1 (8) it is judged that approximately 10 subjects per clinic and 3 clinics is reasonable for detecting any safety issues with the Investigational device in this study. The primary safety evaluation will be performed 3 months post-surgery, which with an estimation of 30 subjects will equate 7.5 patient years. This is considered to be enough safety data for the primary safety analysis.

With a total of 30 subjects, there will be a very high power to detect significant changes in the primary performance evaluations *audiometric thresholds (PTA4)* and *adaptive speech in noise (speech to noise ratio, SNR)*.

PTA4: Assuming the same mean reduction in PTA4 as in the multicentre clinical investigation of the predecessor Osia System (Mean change -25 dB, SD 9.5 dB), the resulting power with 30 subjects is 0.99.

SNR: In the multicentre clinical investigation of the predecessor Osia System a change in SNR from 4.98 dB (SD 7.76 dB) unaided to -8.19 dB (SD 6.58 dB) aided resulted in a mean improvement in SNR of -13.3 dB (SD 8.1 dB). In that investigation, speech was presented from the front and noise from the rear speaker. In the present investigation, however, both speech and noise will be presented from the front speaker, which is known to result in higher SNR values in the aided situation (the SNR in the unaided situation is not expected to change significantly). In a pilot clinical investigation conducted at Cochlear's own research facility (CBAS5271, Sub study 118), a mean SNR value of -2.5 dB was recorded with the Investigational device (Osia 2 System). Assuming that in the present investigation the unaided mean SNR is similar to the unaided scores in the multicenter investigation and that the aided mean SNR is similar to the pilot investigation, a mean improvement in SNR of approximately -7.6 dB (SD 8.1 dB) is expected. With 30 subjects, the resulting power is 0.99.

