#### **3.3.2 Intent-to-Treat**

The Intention-to-Treat population/dataset (ITT) will include all subjects who have undergone surgical intervention.

Missing data will be handled according to 3.4.1.

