### **3.4 Additional Statistical Considerations**

#### **3.4.1 Missing, Unused or Spurious Data**

All ITT analyses will be performed/presented both for the imputed (main analyses) and for the non-imputed data (sensitivity analyses).

Imputation of missing values will be performed for all efficacy variables. No imputation of baseline values or baseline carry forward will be made. Imputations will be made according to the following rules:

1. If a value is missing at the end of a time period for a patient, last observation will be carried forward.
2. If a missing value is occurring between two time points with values, an interpolation will be made for continuous variables and for categorical variables the value from the previous visit will be carried forward.
3. As a sensitivity analysis imputation of missing values will be performed for all efficacy variables using stochastic regression imputations.

Spurious data will be cleaned prior to clean file meeting. If spurious data are detected after clean file is declared actions to consider will be;

1. unlock, correction of the spurious data and a new re-lock will be made alternatively,
2. a sensitivity analysis will be performed that accounts for the spurious data in a proper statistical fashion (e.g. non parametric methods).

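### Does the trial need a written scoring rule for Australian subjects who cannot reach 50% unaided with speech fixed at 65 dB SPL?

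*Protocol*

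**What the plan says.** Protocol 7.3.2.2 uses two versions of the adaptive test. In Melbourne and Sydney (AuSTIN), "The sentences shall be presented at a constant level of 65 dB SPL throughout the test", and the noise moves until half the morphemes are repeated correctly. In Hong Kong (CHINT), "the noise shall be kept constant at 65 dB SPL, and the speech shall be adapted stepwise". In both cases the stepping is left to the test software. The same section refers to a separate, detailed work instruction for the audiological assessments.

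Protocol 9.1 bases the choice of paired tests on complete data: "Since all included subjects will have measurements of the primary and important secondary efficacy variables for unaided hearing". SAP 3.2.3 requires both PTA4 and SNR to be significant at 0.05 two-sided for the primary analysis to be confirmative. The ITT set "will include all subjects who have undergone surgical intervention" (SAP 3.3.2).

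On missing values, SAP 3.4.1 says "No imputation of baseline values or baseline carry forward will be made", as does Protocol 9.1. A missing follow-up value is treated differently: "If a missing value is occurring between two time points with values, an interpolation will be made for continuous variables", and a missing last value takes the last observation.

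**The concern.** With speech fixed, removing all the noise is the easiest condition AuSTIN can offer. A subject still below 50% there has no SNR at which the target is met. In Hong Kong the speech level can rise, so the same limit does not apply in the same way.

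The documents give no noise floor, maximum SNR or failure code. If the result were entered as missing at baseline, the subject would stay in the ITT set but have no change score, in either the imputed or the non-imputed analysis. The same result at 3 months would be filled from other visits. If the software returned a limit instead, the mean and SD would depend on a number that neither document states.

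The subjects at risk are those with the worst unaided hearing at two of the three sites, and SNR is co-primary. At stake would be a selected population for the SNR estimate and an apparent difference between Hong Kong and Australia that comes only from the scoring.

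**Working it through.** **1. The plan's own figure.** Protocol 9.4 and SAP 3.1 assume a mean change of -7.6 dB, SD 8.1, n = 30, and state power 0.99. A paired t-test stands in for the permutation test. The noncentrality is (7.6/8.1)×√30 = 5.14 on 29 df; at two-sided 0.05 the power is 0.9987, so the figure reproduces. The components (4.98 unaided, -2.5 aided) give -2.5 - 4.98 = -7.48, with power 0.9983. The steps below use -7.48.

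**2. Are such subjects plausible?** Yes. Protocol 4.2.2.1.1 reports a mean gain of 59.8 points for words in quiet at 65 dB SPL with the predecessor. An aided score cannot exceed 100%, so the mean unaided score was at most 100 - 59.8 = 40.2%. At 80 dB SPL the range of gains reaches 100 points, so at least one subject scored 0% unaided at a level 15 dB above the AuSTIN speech level. These are words rather than sentence morphemes, so they give no rate.

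**3. What does the largest predecessor SNR change show?** The same section reports "adaptive speech in noise (SNR) of -13.3 dB (SD 8.1, range -47.2 to 0.6 dB". Placing that subject's aided SNR at the group mean gives an unaided value of 47.2 - 8.19 = +39 dB, but a change this extreme implies an unusual aided value too. From the SDs in Protocol 9.4:

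- r(unaided, aided) = (7.76² + 6.58² - 8.1²)/(2×7.76×6.58) = 0.371
- slope of unaided on change = (0.371×7.76×6.58 - 7.76²)/8.1² = -0.629
- expected unaided = 4.98 + (-0.629)×(-47.2 + 13.3) = +26.3 dB; expected aided = 26.3 - 47.2 = -20.9 dB
- conditional SD = 5.85, so P(unaided ≤ +20) = 0.14 and P(unaided ≤ +25) = 0.41

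Bivariate normality is rough this far out. The subject's SNR was recorded as a number, so this is not an example of an unreached target. A printed range also shows only that at least one subject was this extreme; it puts no upper bound on the share affected. The count here is therefore an assumption: k = 1 or 2 of about 20 Australian subjects (about 10 at each of three sites).

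**4. Effect if missing.** Assume the other 30 - k subjects follow the planning figures. The mean stays at -7.48. Power is 0.9977 at n = 29 and 0.9970 at n = 28.

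**5. Effect if scored at a limit L.** A subject with a poor unaided SNR should also have a poorer aided SNR. The slope of aided on unaided is 0.371×6.58/7.76 = 0.315. The improvement beyond the average is (1 - 0.315)×(L - 4.98), and the shift in the pooled mean is k times this, divided by 30. The limits of 15 to 25 dB are assumed.

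| L (dB) | Extra improvement (dB) | Shift, k = 1 | Shift, k = 2 |
|---|---|---|---|
| 15 | 6.87 | 0.23 | 0.46 |
| 20 | 10.29 | 0.34 | 0.69 |
| 25 | 13.72 | 0.46 | 0.91 |

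Dividing by 20 instead of 30 gives the shift in the Australian mean: 0.34 to 0.69 dB (k = 1) or 0.69 to 1.37 dB (k = 2). Giving these subjects an average aided SNR of -2.5 instead would raise the pooled shifts to 0.33-0.67 and 0.67-1.33 dB.

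**6. Opposite direction.** Suppose the target is not reached with the device either, so that a limit would score no change. The full mean would be -7.48×29/30 = -7.23 dB (k = 1) or -7.48×28/30 = -6.98 dB (k = 2). Dropping these subjects would overstate the gain by 0.25 or 0.50 dB. Keeping them as zeros leaves power at 0.996 or 0.995.

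**7. Stress case.** Simulating from the same SDs and r, and deleting the worst unaided scores among 20 Australian subjects, gives a mean of -6.86 dB and power 0.993 for two deleted, and -6.00 dB and 0.952 for six. Deleting ten (run at -7.6 dB) gives -5.55 dB and 0.85. With six deleted, subjects with measurable SNRs down to about +10 dB are already being removed, so this is a bound and not a forecast.

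**The case for a change.** The strongest argument for acting is that a rule deciding who enters a co-primary comparison, or with what value, should not sit outside the SAP. The documents' own quiet-speech data make affected subjects realistic, and Protocol 9.4 expects no relief in this trial: "the SNR in the unaided situation is not expected to change significantly". One clinical result would be handled in opposite ways at baseline and at 3 months. The remedy would be cheap: a sentence of SAP wording and perhaps a source-data query.

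Much of that stands. The silence is real, and a sentence would do no harm. It does not follow that the plan is deficient without one. The scoring of an adaptive track is a property of the test, and the protocol assigns it to the software and the work instruction. Those are not among the documents, so the absence of a rule cannot be inferred. A limit of 15 to 25 dB chosen in the SAP would itself be arbitrary: in the two-deletion stress case the removed baselines reach down to about +16 dB, so a limit of 15 would rank a subject who cannot reach 50% above subjects who can.

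Any loss would also be visible. SAP 3.7.1 reports n, median, minimum and maximum. Table 14.2.2.6 gives speech in noise by site, and Protocol 9.9 adds a site tabulation without testing. The analysis sets are settled at the clean file meeting before database lock, where a missing co-primary baseline would be noticed.

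**Conclusion.** This is a gap that the test procedure and the analysts can fill sensibly; the plan need not change. Harm requires at least one Australian subject below 50% without noise and a decision to code that result as missing. Neither is shown, and the count may be zero.

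For one or two such subjects who reach 50% with the device, a missing code would understate the pooled SNR improvement by 0.23 to 0.91 dB, which is 3% to 12% of 7.48 dB. If they do not reach it with the device, the mean would be overstated by 0.25 to 0.50 dB. In every one- or two-subject case computed here, power is 0.995 or more, so the confirmative conclusion would not be expected to change. By-site differences carry no test.

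These sizes assume about 20 Australian subjects, the planning means and SDs, a bivariate normal relation with r = 0.371, a t-test in place of the permutation test, and limits of 15 to 25 dB. The number affected is the weakest input. Only if many Australian baselines were lost (six or more in the stress case) would the estimate move by about 1.5 dB and power fall towards or below 0.95, and the planned counts by site would show that.
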